9. DETAILED DESCRIPTION OF METHODOLOGY

9.1. REIMBURSEMENT

Participants will be reimbursed for parking at all study locations (McMaster University) should they decide to attend the visits in person. Participants will be provided with an honorarium of \$20 for their involvement in the study. If participants in The App group use their own phone, they may be provided up to \$25 in compensation for data usage on their cellular device.

9.2. RISKS

Some participants may experience worsening of post-concussion symptoms during the completion of the study, due to physical or cognitive exertion (headache, dizziness, nausea etc.). In the event of worsening post-concussion symptoms, use of The Back2Play App will be immediately stopped and resumed only after a minimum period of 24 hours of rest and a resolution of symptoms. If participants do not want to continue with the testing, there will be no negative consequences. In addition, some participants may feel anxious about using The Back2Play App and their performance. The Research Team will explain the use of The Back2Play App in detail and will take special care to emphasize that results will be completely confidential and not shared with anyone outside of the Research Team.

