Rules, precedingly referred to as 'business rules', were developed for in App notifications that follow the guidance of the RTA/RTS protocols for progression through the stages (Appendix 1.1) Symptoms, self reported stages and activities are measured daily in the morning, afternoon and evening. A summary of these surveys is found in appendix 1.2. The home screen of the App (appendix 1.3) summarizes the next survey time, current stage of return to school and activity the youth is reporting that day and the activity minute goals (based on their stage of recovery) and how many activity minutes are completed. Icons at the bottom direct users to 1) a summary page that will show this information as well as a graph of their current symptoms, 2) a charts page which has several graphs of their progress (symptoms, stages, heart rate and activity minutes), 3) resources including the CanChild guidelines for concussion recovery, symptom strata (or the type of recovery pattern they may be following), the playsafe cards for individual sport specific strategies and a list of activity suggestions for each stage of recovery and 4) a contact us page which gives the Research Team [contact] and Principal investigator contact info as well as a form for troubleshooting help. When youth fill out the surveys, if 2 or more symptoms are worse, a pop up option of texting or emailing the participant's parent appears (appendix 1.3) Notifications are also sent to youth who exceed their activity goals and the Back2Play App will send a cautionary message "You are doing too much!" if their heart rate goes above 180. Encouraging notifications are also programmed with business rules if participants stay in the same stage for extended periods or if their symptoms get worst.

A complimentary App was developed by [name] of our investigator team. This Brain Games App was designed to screen some typical neurocognitive functions affected by concussion. There are 5 "games" that take about 10 minutes to complete. These include 1)

finger-tapping, 2) divided attention, 3) memory for designs, 4) tracing and 5) face match. An 'in App notification' is triggered by the youth recording a progression in their RTS stage. "Let's do a brain teaser! Sign into The Back2Play Brain Games App for your brain game then complete your symptom survey!" If the challenging tasks result in increased symptoms, The App notifies them "The brain game can be hard, stay at this stage if you need too!"

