7. INTERVENTIONS

Participants randomized to the control group will be provided Usual Care which often is some type of gradual return guidelines the practice (ED, General Practitioner) subscribes to. These are usually provided in a paper format for the patient to take home. Participants in the Usual Care group will complete symptom surveys every 24 hours via REDCap. The Back2Play App requests symptom surveys be done 3 times daily (quickly done on the watch or phone). The Back2play App also asks users to go to the BrainGames App when participants indicate they are ready to progress to the next stage of RTS in the guidelines. In The BrainGames App they can complete 5 neuropsychological tasks that provide feedback about their readiness to progress. These tasks are not available for those in the Usual Care group.

Surveys about cognitive and physical activities engaged in as well as the participants self-rating of cognitive activity level (1-5) and stage of recovery (1-5/6) are done on a daily basis by both groups.

Participants who have been randomized to the App group will be asked to:

- Download The Back2Play App and The B2P BrainGames App on their iPhone and the Apple Watch provided either at the ED or at a scheduled baseline visit (within 2 days of concussion).
- Pair the Apple Watch to their iPhone and wear an Apple Watch for the duration of the study.
- Complete the initial post-concussion symptom survey on the App with the Research Assistant and receive orientation to The Back2Play App.
- Complete 3 symptom surveys per day on The Back2Play App (Morning, Afternoon and Evening) and daily surveys about cognitive and physical activities as well as self-rating of participants' own cognitive level of activity and stage of concussion recovery until 2 days following symptom resolution.
- Complete games on the B2P BrainGames App (i.e. matching games) which are suggested whenever the participant moves up a stage in RTS Protocol.
- Attend a Zoom Follow Up meeting 2 days after symptom resolution or after a maximum of 3 months of using The App. Here, we will ask participants questions about their perceptions of how well The App guided them through their recovery. Did they agree with classifications and notifications, did they understand the guidelines as well as questions about any other interventions they may have received. This Zoom visit will be recorded and saved to a secure, password encrypted study computer.

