Appendix 1.1 Business Rules for In-App Notifications

Progression through the CanChild RTA/RTS Guideline

- 1. Participants cannot enter RTA Stage 4 until they have completed RTS Stage 1-3
 - o If the participant reports RTA Stage 4 when they are in RTS Stage 1 or 2 they will receive the message "Stage 1, 2 and 3 come before RTA Stage 4!"
- 2. Participants must complete RTS Stage 5 (Full Return to School) before they can enter RTA Stage 4.
 - If the participant reports RTA Stage 4 or 5 when they are in RTS Stage 3 through 5, they will receive the message "You should complete RTS Stage 4-5 before RTA Stage 4-6".
- 3. Participants will be recommended to move to Stage 2 of RTS after 7 days
 - o If the participant reports RTS Stage 1 for 7 days, they will receive the message "You reported being in Stage 1 for 1 week, time to move to Stage 2!"
- 4. Participants will be recommended to move to Stage 3 of RTS after 14 days
 - o If the participant reports RTS Stage 2 for 14 days, they will receive the message "You reported being in Stage 2 for 2 weeks, time to move to Stage 3!"
- 5. Once in RTS Stage 3, participants cannot move back to Stage 2.
 - o If the participant reports RTS Stage 3 and moves back to RTS Stage 2, they will receive the message "Once your reach RTS Stage 3, you should not return to RTS Stage 2".

- 6. Participants are recommended to complete RTA and RTS Stage 1-3 together.
 - o If the participant reports RTA Stage 3 while in RTS Stage 1 or 2, they will receive the message "Remember, RTS and RTA Stage 1 to 3 should go together!"
- 7. Participants will be cautioned when they try and skip a stage
 - o If the participant skips from RTS Stage 2 to RTS Stage 4, they will receive the message "You forgot RTS Stage 3, we recommend you log this stage first!"
- 8. Participants will be cautioned when they try to move back a stage.
 - o If the participant moves back a Stage i.e., RTS Stage 5 to Stage 4, RTA 5 to Stage 4 they will receive the message "*Are you sure you want to move back a stage?*"
- 9. Participants cannot progress to a new stage of RTA/RTS if 2 or more symptoms worsen
 - o If the participant reports that 2 or more symptoms worsen (from morning to evening survey), **and** the participant attempts to progress to a new stage, they will receive the message "We recommend you do not progress to a new stage and inform a parent of your symptoms".

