- 10. Participants cannot progress to a new stage of RTA/RTS if their total number of symptoms increases by 2.
 - o If the participant reports an increase in symptoms by 2 (from morning to evening survey) **and** the participant attempts to progress to a new stage, they will receive the message "We recommend you do not progress to a new stage and inform a parent of your symptom".

CanChild RTA/RTS Symptom Strata

- 11. Participants will be classified to Strata A (Symptom Free within 48 hours after Injury) if their initial symptoms disappear within 24 hours or after 24-48 hours a participant reports ≤ 2 symptoms.
 - o If symptoms worsen, a participant can transition to Strata B.
 - o If the participant reports that their symptoms disappear within 24 hours, they will receive the message "Take at least 24 hours for each Stage as you complete the guidelines".
- 12. Participants will be classified to Strata B (Symptom Free/Symptoms decreases within 1-4 weeks post injury) if the report > 2 initial symptoms at 50 hours and continue at > 2 for 1 week (168 hours) up to 4 weeks. If the child's symptoms decrease, but are still >2, the child should remain in stratum B.
 - o Once a participant is in Strata B, they can never go to Strata A.
 - o If a participant is in Strata B and progressing through Stages within 2 days, but symptoms are getting worse, the child should take longer to progress through the stages.
 - o If > 2 Symptoms for a month, move the participant to Strata C

- o Recommendation: "Take at least 48 hours for each Stage as you complete the guidelines".
- 13. Participants will be classified to Strata C (Symptomatic for more than 4 weeks) if they report ≥ 2 initial symptoms for ≥ 4 weeks, or if the participant has been in Strata B for 1 month.
 - Once a participant is in Strata C, they can never go to Strata A or B.
 - o Recommendation: "Take at least 1 week for each Stage as you complete the guidelines".

Increasing or Worsening Symptoms

- 14. Participants will be reminded to share their symptoms with their parents if their number of symptoms increases by 2
 - o If the participant reports 2 or more symptoms new symptoms, they will receive the message "We recommend you inform a parent of your symptoms".
- 15. Participants will be reminded to share their symptoms with their parents if 2 or more symptoms worsen.
 - o If the participant reports 2 or more symptoms worsen, hey will receive the message "We recommend you inform a parent of your symptoms".

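### Stopping the Back2Play App when symptoms worsen (section 9.2) conflicts with App rule 16 and the three-a-day survey schedule, and would interrupt guidance and symptom data in the App arm only

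*Combined protocol and SAP*

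**What the plan says.** Section 9.2 (Risks) first describes worsening caused by physical or cognitive exertion. Its rule then begins "In the event of worsening post-concussion symptoms, use of The Back2Play App" and continues: "Back2Play App will be immediately stopped and resumed only after a minimum period of 24 hours of rest and a resolution of symptoms". It sets no threshold for worsening, does not say what counts as resolution, and does not mention surveys.

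Section 7 (Interventions) asks App participants to "Complete 3 symptom surveys per day on The Back2Play App (Morning, Afternoon and Evening) and daily surveys about cognitive and physical activities", until 2 days after symptom resolution. It mentions no pause.

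Section 8 (Measures, Symptoms) has symptoms assessed on the App in the App group and through REDCap in Usual Care. Section 7 has the Usual Care survey emailed every 24 hours. Time to symptom resolution is one of the two primary outcomes in section 8.

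Appendix 1.1 sets out what the App does when symptoms worsen:

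- Rule 9: "Participants cannot progress to a new stage of RTA/RTS if 2 or more symptoms worsen". Rule 10 is similar for an increase in the number of symptoms.
- Rule 11: "If symptoms worsen, a participant can transition to Strata B".
- Rule 12, on a youth in Strata B: if "progressing through Stages within 2 days, but symptoms are getting worse, the child should take longer to progress through the stages".
- Rules 14 and 15: messages to inform a parent.
- Rule 16: a message to slow down, sent when two or more symptoms are reported worse at all three surveys of one day.
- Rule 18: a message to slow down if activity limits are exceeded and symptoms increase.

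None of these rules tells the youth to stop using the App.

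**The concern.** The App is both the intervention and the instrument that records symptoms in its arm. A rule that switches it off when symptoms worsen removes the guidance at the moment it was designed to respond. It also removes the symptom record in that arm, with no substitute described. Usual Care has no matching interruption.

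The gaps would not be random. They would start because symptoms worsened, and they concern a primary outcome that is derived from symptom reports. Section 9.5 plans survival curves and Cox regression and gives no rule for missed surveys. That omission applies to both arms, but it leaves the team with no stated way to handle one-sided gaps.

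**Working it through.** The plan gives no figure on this point to reproduce. The check sets the texts side by side and then works out the survey spacing.

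**1. Which rules conflict with the stop**

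- *Rule 16 conflicts.* It needs three worse reports in one day. If the App stops at the first worse report, for at least 24 hours, the second and third surveys of that day cannot be completed.
- *The section 7 schedule conflicts.* Three App surveys a day until 2 days after resolution, with no pause, cannot be met while the App is stopped.
- *Rules 9, 10, 14, 15 and 18 and the parent pop-up in section 2 do not have to conflict.* Each can fire on the report of worsening, and a stop can follow. They give a different response to the same event.
- *Rules 11 and 12 do not have to conflict.* The move to Strata B is permitted rather than required and can be made on that report. A day of rest is compatible with taking longer over the stages.

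**2. Survey spacing if resolution means that the flare settles**

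The documents give no clock times. Two schedules are assumed:

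- A = 08:00, 14:00, 20:00 (three a day, section 7)
- B = 08:00, 20:00 (the fixed morning and evening symptom slots in Appendix 1.2)

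Gap = first survey at or after the end of the stop, minus last survey at or before its start. Examples under A, for a 24-hour stop:

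- Stop right after the 08:00 survey: the 14:00 and 20:00 surveys are lost, the next is 08:00, and the gap is 24 hours.
- Stop at 10:00: the 14:00, 20:00 and 08:00 surveys are lost, the next is 14:00, and the gap is 30 hours.
- Stop at 22:00: the 08:00, 14:00 and 20:00 surveys are lost, the next is 08:00, and the gap is 36 hours.

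Excess = gap minus the 24-hour Usual Care interval.

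| Length of stop | Gap, stop starts at a survey | Gap, stop starts between surveys | Excess over Usual Care |
|---|---|---|---|
| 24 h | 24 h (A loses 2, B loses 1) | 30–36 h (A loses 3, B loses 2) | 0–12 h |
| 48 h | 48 h (A 5, B 3) | 54–60 h | 24–36 h |
| 72 h | 72 h (A 8, B 5) | 78–84 h | 48–60 h |

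These are intervals between surveys, not errors in the endpoint. A youth who is symptomatic when the stop begins, and back at that same level when it ends, has generally not reached the endpoint in between. The recorded date then does not move. It can move only if final resolution falls inside a stop, and then by no more than the gap.

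**3. If resolution means full resolution**

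The App stays off from the worsening until the endpoint has occurred, with no App symptom report in between. Two later points can bound the date. One is the resumption of the App, which 9.2 makes conditional on resolution. The other is the follow-up contact, which section 7 times at 2 days after resolution or at a maximum of 3 months. The prompts in Appendix 1.6 ask whether symptoms remain, not when they ended. The event is therefore interval-censored between the stop and the earlier of those two points.

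**The case against.** The best defence is that 9.2 is a precaution about exertion. It follows a sentence on physical or cognitive exertion, and it goes on to speak of testing and performance, which suggests a task session such as the Brain Games. It never says that surveys stop. On the flare reading, the minimum stop can cost nothing relative to the Usual Care interval. Keeping a screen in use during a flare is also not plainly better, since the lowest level of the study's own cognitive scale excludes screen time.

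Much of this stands. The loss of surveys is an inference from the fact that they are done on the App. But the text names the Back2Play App, not the Brain Games. Section 2 already handles symptoms brought on by a game differently, with a symptom survey and a message about staying at the current stage.

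Three stronger readings are tempting, and the documents do not support them:

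- *That 9.2 contradicts all the App's worsening rules.* Only rule 16 and the section 7 schedule are incompatible with it. The others could coexist with a short pause.
- *That the 24–84 hour gaps measure error in time to symptom resolution.* They measure survey spacing.
- *That on the full-resolution reading only the closing interview could date the endpoint.* Resumption of the App would also bound it.

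**Conclusion.** The point holds as a conflict in the current text with a one-sided consequence. Staff cannot follow 9.2 together with rule 16 and the section 7 schedule. If they follow 9.2, guidance and symptom data are interrupted in the App arm only, at times that depend on symptoms.

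The effect on the primary outcome depends on an undefined word. On the flare reading, which is the more natural one, it is small and arises only when final resolution falls inside a stop. On the full-resolution reading it is substantial for each youth affected, because the endpoint date is known only within an interval that starts at the stop.

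The documents do not say how often or for how long the App would be stopped, so the overall size cannot be given. A demonstrated bias in the treatment comparison is not established. The conclusion assumes that stopping App use also stops its surveys, and the hour figures assume the clock times shown.

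**What to change.** Amend section 9.2 along these lines: when symptoms worsen, the youth stops the exerting activity and the Brain Games and rests for at least 24 hours, until symptoms are back to their level before the worsening. Symptom reporting continues at least once every 24 hours throughout, on the App or, if the App must be paused, through the existing REDCap symptom survey.

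If a pause of the App is kept, the same paragraph should define worsening (for example by the two-symptom threshold of rules 14 and 15) and say that the pause takes precedence over rule 16 and the section 7 schedule.

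The cost is one paragraph and any matching consent text. The REDCap symptom survey already exists for Usual Care, and section 8 already has both groups complete the cognitive scale through REDCap once a day. The downside is a brief daily survey during a flare, the same as Usual Care participants already complete. The rest precaution is kept, and sample size and visits do not change.

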9.3. BENEFITS

The potential benefits of carefully monitoring youth to control their activity level and better follow the protocols for restricted activity is that youth and their families will be better informed about their concussion symptoms and level of activity. Close monitoring will also alert the family, the youth, school and the Research Team of any concerning symptoms and need for intervention. Adhering to the RTS/RTA protocols may help prevent the youth from returning to activity before they are ready, and this can help to prevent further injury to a vulnerable recovering brain.

9.4. STUDY WITHDRAWAL

Participants can withdraw from this study at any time. They may contact the Principle Investigator/Research Coordinator to let them know they wish to no longer participate. Participants will be made aware that they can withdraw at any time and there will be no negative consequences. Immediately following study withdrawal, participants in The App group will be directed to unpair the watch from their personal phone if used and remove the App. Study equipment (phone, watch) will be returned by the participant either by provided Fedex postage or drop off at The McMaster Institute for Applied Health Sciences.

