3. METHODS

Description of Population and Sample

Our population consists of male and female youth aged 10-18 years that have been diagnosed with a concussion by a physician. Youth presenting to the David Braley Clinic, McMaster Children's Hospital, HWCDSB, Montreal Children's Hospital or physicians in the community will be randomly assigned to the intervention or control groups.

A clinically significant effect of 10% decrease in repeat head injury and 10% decrease in recovery time would be of interest. The sample size calculation was done using parameters with a two sided significance of 0.05 and a power of 0.8 and based on our primary outcome of repeat head injury which is a binomial variable. Our anticipated incidence rate was compared to two rates of incidence in clinical settings and in the literature:

- 16% rate common in the literature
- our anticipated 2% rate with adherence to protocols (from previous B2P study) N=128
- 37% rate from concussion clinic at MCH and
- 13% rate of our pilot data N=100.

The larger number will be sought (sample size takes into consideration 20% refusal rate and loss to follow up) therefore we will recruit N=160. With an average of 25-30 new cases per month from the sources outlined above, 60% consent rate, and 12 months recruitment, it is feasible to attain this sample of youth.

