- Complete the (SUS) after they have finished using the App (Appendix 1.5). Participate in a Follow Up interview (Appendix 1.6) which will assess the youth's experience with their recovery using The Back2Play App, ask about any other interventions they had and if they have experienced a repeat injury during the time in the study.
- Delete the App from their phone during this interview and arrange to return (by scheduled pick up or FedEx label sent by The Research Assistant) device(s).
- 3 months following study enrollment, participants will be sent a survey through REDCap about reinjury to complete.

Participants who have been randomized to the usual care group will be asked to:

- Receive the usual course of care given by the hospital, General Practitioner or clinic which may or may not include written guidelines, suggestions or resources
- Complete the initial post-concussive symptom survey with The Research Assistant.
- Complete symptom surveys and daily surveys about cognitive and physical activities as well as self-rating of participants' own cognitive level of activity and stage of concussion recovery every 24 hours emailed by REDCap until 2 days following symptom resolution.
- Participate in a Zoom visit 2 days after symptom resolution or after 3 months of
 participation for those who do not achieve symptom resolution. Participants will
 be asked questions regarding their knowledge of and ability to follow the Usual
 Care guidelines they received and about any other interventions they may have
 received. This Zoom visit will be recorded and saved to a secure, password
 encrypted study computer.
- 3 months following study enrollment, participants will be asked to complete a survey about reinjury.

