8. DESIGN

Phase 3 of this study has both quantitative and qualitative components. The aims of the qualitative components of the study are to determine if participants liked using The App, and if their experiences of using it helped their recovery from concussion. In addition, qualitative data will be used to review any improvement suggestions to The App before commercialization. Using both qualitative and quantitative research methods we will explore

the usability of The Back2Play App components under consideration for the final version of the App to be commercialized.

Primary Research Outcomes

To assess:

- Risk for repeat head injuries within three months of study completion (3-6 months after injury)
- Duration of symptoms: Time to symptom resolution from date of injury

Secondary Research Outcomes

To assess:

- 1) The frequency of symptoms using PCSS.
- 2) Time to return to activity and time to progress through the 6 stages of RTA
- 3) Perceptions of the platform by parents and youth.
- 4) Accuracy of the algorithm embedded in the background of The App classifying the participant's stage of recovery

Measures

Symptoms

Concussion symptoms will be assessed on The Back2Play App for those randomized to The App group and via REDCap for those randomized to Usual Care. A modified version of the PCSS (consisting of 22 symptoms) will be completed by youth in both groups. The Likert scale was modified to detect the presence of symptoms rather than symptom severity. Symptom data will be collected 3x/day for participants using The Back2Play App and every 24 hours for participants in the Usual Care group.

Cognitive Activity

Cognitive activity will be assessed using a modified version of the scale developed by Brown et al. Participants in both groups will be asked to complete this scale once per day through REDCAP which will appear as follows:

"Please rate 1-5 what you've been doing today"

- 1- None- No reading, homework, text messaging or screen time (T.V., cell phone), can talk on phone
- 2- Minimal- 15 minutes of screen time or schoolwork 2x daily. Socialize with 1-2 friends, no longer than 30 minutes,
- 3- Moderate- Homework in 15 minutes blocks for a maximum of 45 minutes. Screen time/T. V in 15-minute blocks, for up to an hour daily.
- 4- High- Complete as much homework as tolerated. 1 test/week or tests with accommodation (i.e. longer time to write), less reading, homework and screen time than normal
- 5- Full- no restrictions to cognitive activity

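### A youth who stops using the App has no other way to report symptoms, so time to symptom resolution can be cut short by a mechanism that exists only in the App arm

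*Combined protocol and SAP*

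**What the plan says.** **Where symptoms are recorded.** Section 8 (Measures, Symptoms): "Concussion symptoms will be assessed on The Back2Play App for those randomized to The App group and via REDCap" for Usual Care. Section 7 has App youth wear the watch throughout and answer three symptom surveys a day in the App. Usual Care youth get one emailed REDCap survey a day. Both continue until two days past symptom resolution.

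**How a youth leaves.** Section 9.4 covers one event, telling the team that they no longer wish to take part. It then states: "Immediately following study withdrawal, participants in The App group will be directed to unpair the watch". The unpairing applies where a personal phone was used. The App is also removed and study equipment returned.

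**Other stops.** Section 9.2 has a temporary pause of App use when symptoms worsen, and says that not wishing to continue has no negative consequences. Neither statement names another way to report symptoms.

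**Re-injury.** Section 7, App arm: "3 months following study enrollment, participants will be sent a survey through REDCap about reinjury to complete". Section 8 puts the re-injury questions to all participants, and the interview in Appendix 1.6 asks everyone about another blow to the head.

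**Analysis.** Section 9.5 uses Cox regression for time to symptom resolution. It has no intention-to-treat statement, censoring rule or missing-data rule, and it describes the baseline comparison by use of the App rather than by allocation.

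**The concern.** In most trials a participant can stop treatment and still be measured. Here stopping the App also switches off the measurement. A youth who tires of the watch or the prompts, but would answer a short email, has no route for doing so.

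Time to symptom resolution is a primary outcome and depends on regular symptom reports. If reports end before resolution, the date is unknown. Stopping a recovery-guidance device may well be related to how recovery is going. Censoring such youth as uninformative then compares a selected part of the App arm with a Usual Care arm that has no corresponding mechanism. Analysing by allocated arm cannot restore dates that were never collected.

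**Working it through.** **1. The same behaviour in each arm.**

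| Step | Usual Care youth stops following the guidelines | App youth stops using the App |
|---|---|---|
| Symptom instrument | Emailed REDCap survey, still arriving (Section 7) | The App, no longer used (Section 8) |
| Alternative route described | None needed | None |
| Resolution date | Still obtainable | Not obtained if symptoms persist at stopping |
| 3-month re-injury survey | Scheduled from enrolment | REDCap, scheduled from enrolment, App not needed |

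The closing interview does not replace the symptom record. Appendix 1.6 asks about current symptoms, but no listed question asks when they ended. In the App arm its timing also depends on symptom resolution or on three months of App use, and for a stopper neither may be observed.

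**2. What the sample size covers.** Section 3 sizes the trial on re-injury, 16% against 2%, with "two sided significance of 0.05 and a power of 0.8". For two proportions with pooled variance under the null:

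n per arm = [1.96 × √(2 × 0.09 × 0.91) + 0.842 × √(0.16 × 0.84 + 0.02 × 0.98)]² / 0.14² = 64.4, so 65 per arm and 130 in all, against 128 stated.

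Then 128 / 0.8 = 160, as stated, or 80 per arm. The plan's figure reproduces. Its 20% is one allowance for refusal and loss combined, not split by arm or reason. It protects numbers, not comparability. No calculation is given for time to symptom resolution.

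**3. Scale under assumed stopping rates.** The documents give no rate of stopping the App. I assume 10%, 20% or 30% of 80 App youth stop while symptomatic: 8, 16 or 24 youth without a resolution date.

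**4. Why the direction is open.** Suppose the App has no effect. Take from the Background the 59% of children still symptomatic at one month. This is only a reference value: that cohort is not the trial population, and the trial enrols up to a month after injury. Let a share x stop at the outset, and let q be the proportion of them truly symptomatic at one month. The App-arm estimate is then (0.59 − x·q) / (1 − x).

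| x | q = 1 (all stoppers still symptomatic) | q = 0.59 (like the rest) | q = 0 (all stoppers recovered) |
|---|---|---|---|
| 10% | 0.49 / 0.90 = 54.4% | 59% | 0.59 / 0.90 = 65.6% |
| 20% | 0.39 / 0.80 = 48.8% | 59% | 0.59 / 0.80 = 73.8% |
| 30% | 0.29 / 0.70 = 41.4% | 59% | 0.59 / 0.70 = 84.3% |

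These are outer limits, because both values of q are extremes and stopping at the outset is the worst case. The true value of 59% lies inside every band. The App could look better, worse or unaffected, depending on who stops.

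**The case against.** Several stronger readings are tempting, and the documents do not support them.

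- *Stopping the App counts as withdrawal.* A reader might infer this because 9.4 describes no other exit. Its trigger is a wish to leave the study. A youth who stops logging without asking to leave appears to stay enrolled.
- *Both primary outcomes are lost.* Nowhere is it said that the re-injury survey is withheld. App youth who recover early delete the App at the closing interview, and the REDCap survey still follows three months after enrolment. Re-injury is at risk only if a stopper is handled as fully withdrawn, and 9.4 is silent on later contact.
- *Only the App arm loses data.* Usual Care youth can also withdraw or stop answering, in an unblinded trial. What is confined to the App arm is loss caused by giving up the device.
- *The App youth who remain are the quicker to recover.* This is a guess. Youth who feel well may drop the App first.
- *A biased re-injury odds ratio can be calculated.* That needs an assumed stopping rate and assumed risks in those lost, for the outcome least affected.

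It is also fair that Cox regression handles youth without an observed event, that reports up to stopping are kept, that Section 7 describes the App surveys as quick to complete, and that Section 2 of the pilot history in the introduction reports high satisfaction. The consent forms are not in the public file and may set terms for contact after withdrawal.

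These points narrow the issue but do not remove it. Censoring is safe only if stopping is unrelated to recovery, and no passage gives a stopper who stays enrolled another way to report symptoms.

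**Conclusion.** The point holds for symptom data. As written, stopping the App ends symptom reporting, and so truncates time to symptom resolution through a route with no counterpart in Usual Care. Section 9.5 would by default censor these youth as if stopping were uninformative.

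The size and direction of any bias cannot be derived from the documents. The counts of 8 to 24 youth and the bands above rest on assumed stopping rates and extreme assumptions about stoppers. They show what is left open, not what will happen. Re-injury is a secondary exposure that turns on how 9.4 is applied. This is a worthwhile change made before data are lost, not evidence that the trial's result will favour the App.

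**What to change.** In Section 9.4, separate stopping use of the App from withdrawing from the study.

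- By default, a youth who stops the App returns any loaned device and moves to the Usual Care REDCap daily symptom survey until two days past symptom resolution. The closing interview and the 3-month re-injury survey are kept.
- A youth who declines daily surveys is asked for the date symptoms ended, as one item added to the 3-month survey.
- The date and reason for stopping are recorded.
- Data collection ends only when the youth withdraws from follow-up.
- Section 9.5 states that all youth are analysed by allocated arm.

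The cost is protocol and consent wording and the use of an existing REDCap form for App youth. Follow-up without the App is already part of the plan, since the 3-month survey reaches App youth by REDCap. The downside is that a few youth who leave the App receive further survey emails. The right to withdraw is unchanged.
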